8.7.5 BAX 855 Prophylaxis Dosing

FVIII trough level of 1-3%:

BAX 855 will be administered twice weekly, with either:

- Infusion with alternating 3- and 4-day infusion intervals; the doses will be different if a 3- or a 4-day interval needs to be covered
- An infusion every 3.5 days
- Depending on subject's individual PK, different dosing intervals should be considered, in particular if single doses of 80 IU/kg are required or regular FVIII peak levels of 200% would be reached or exceeded

^{vi} In case a subject underwent a PK determination in any of the BAX 855 studies, the PK assessment may have to be repeated based on the sponsor's evaluation.

FVIII trough level of approximately 10% (8%-12%):

- BAX 855 will be infused every other day.
- Depending on subject's individual PK, a different dosing interval may be considered to prevent regular high FVIII peak levels

The required dose and frequency will be provided by the sponsor. Subjects must adhere as closely as possible to the dosing regimen. If a dose is missed, it must be documented and the next dose will be taken as soon as possible. After this dose, the regularly scheduled regimen will be resumed. Subjects requiring treatment for a breakthrough bleeding episode should resume their PK-tailored prophylaxis as soon as the bleeding episode is resolved.

The days of the week on which treatment is administered may be selected by the subject and/or his/her physician and should provide maximum coverage for vigorous activities. To provide some flexibility, the weekly schedule in terms of the days of the week may be changed during the course of the study to best accommodate potential changes in the subject's life style. However, the initially calculated and adjusted, if applicable, dose regimen should be maintained.

For each subject, the BAX 855 infusions to perform PK(s), IRs and the first individualized prophylaxis dose of BAX 855 at the Baseline visit, which includes an IR assessment, must be administered in the hospital/clinic setting under medical supervision. All other treatments may be self-administered, administered by a parent or caregiver, or administered in the clinic or hospital setting. Each subject's physician will determine the setting of treatment administration. If the subject will self-administer BAX 855, the investigator will ensure that the subject and/or his caregiver have been adequately trained.

The weight determined at baseline and subsequent study visits will be the basis for dose calculation of BAX 855 and recalculation, if applicable.

8.7.6 BAX 855 Dose and/or Frequency Adjustments

In the first 6-month treatment period the regimen may be adjusted based on the FVIII trough level determined at each study visit. FVIII trough levels should always be determined immediately before the planned next scheduled prophylactic infusion which may coincide with an infusion for determination of IR.

Before dose adjustment, if applicable, a confirmatory FVIII trough level determination at an additional study visit within 2 weeks after receipt of the FVIII activity results has to be

performed^{vii}. This additional study visit should also occur after a washout period which is consistent with the infusion interval according to the treatment regimen provided to the subject and immediately before the next planned regular prophylactic infusion. After receipt of the repeat FVIII activity results, dose adjustments should be performed:

- If the lower FVIII trough activity level is <1% and <8% respectively;
- If the upper FVIII trough activity level exceeds 3% and 12% respectively. Given the assay variations, fluctuations of approximately 3% are possible.

Approximately 2 weeks after the dose adjustment, a repeat FVIII trough level determination at an additional study visit has to be performed, if it does not coincide with the next scheduled study visit. The blood draw for the FVIII trough level measurement should occur after a washout period consistent with the infusion interval according to the treatment regimen provided to the subject and immediately before the next planned regular prophylactic infusion.

Dose adjustments in the second 6-month period may only be performed if FVIII trough levels are considerably below the required FVIII trough levels of 1% and 8%. Should the upper limit considerably exceed 3% and 12% respectively, a dose adjustment may be performed. Dose adjustments should only be performed in case out-of-range FVIII trough value is confirmed with a repeat FVIII trough level measurement.

Guidance for dose adjustment:

- In case of FVIII levels <1% in the low dose arm, the dose should be increased by approximately 30%
- For FVIII levels >3% in the low dose arm, or FVIII levels >12% or <8% in the high dose arm, the adjusted dose for an infusion interval τ will be calculated as follows:

$$Dose_{adj,\tau} = \left(\frac{TL_{target}}{TL_{predicted,\tau}} \right) * Dose_{current,\tau}$$

where TL_{target} is the target trough level (1.7% or 10%) and $TL_{predicted,\tau}$ is the TL predicted for an infusion interval of τ under the current dose for this interval. The latter will be calculated as:

$$TL_{predicted,\tau} = 0.5 * \left(\frac{Dose_{current,\tau}}{Dose_1} * TL_{measured,t1} * 2^{\frac{t1-\tau}{HL}} \right) + \frac{Dose_{current,\tau}}{Dose_2} * TL_{measured,t2} * 2^{\frac{t2-\tau}{HL}}$$

^{vii} This additional visit may coincide with regular scheduled study visit.

where $Dose_1$ and $Dose_2$ are the actual doses (in IU/kg) of the infusions after which the trough levels $TL_{measured,t1}$ and $TL_{measured,t2}$ were measured, $t1$ and $t2$ are the times in hours post start of infusion for each trough level collection, τ is the infusion intervals for which the prediction is being made, and HL is the terminal half-life of the initial PK assessment.

In case the FVIII levels are below the required lower limit, the BAX 855 dosage may be increased up to a maximum of 80 ± 5 IU/kg and/or the dosing frequency may be increased. Doses as high as 80 IU/kg may be used, provided the FVIII peak level does not exceed 200%. Otherwise, the frequency of prophylactic infusions has to be increased.

In subjects with severe hemophilic arthropathy and/or target joints^{viii} who continue to experience recurrent bleeding episodes, an imaging technology such as magnetic resonance imaging (MRI) or ultrasound of the affected joint(s) has to be applied to verify the presence of a bleed.

Also, if at any time during the course of the study, a subject starts to experience an unexpected high bleeding rate or experiences bleeding episodes that do not adequately respond to BAX 855 therapy, he/she will be evaluated for the presence of inhibitory and total binding antibodies to FVIII, BAX 855 and PEG, and clinically managed at the discretion of the investigator. It is also recommended to perform an IR determination.

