12.3 Trough Levels

At study visit Week 4 \pm 5 days, Week 8 \pm 1 week, and Month 4.5 \pm 2 weeks, FVIII activity trough levels will be measured to ensure that FVIII trough levels are within their targeted range. The blood sampling for FVIII activity, TGA parameters and VWF antigen should be performed immediately prior to the next regular prophylactic infusion, thus maintaining the treatment regimen-specific interval defined for each subject. Following dose adjustments, a FVIII trough level has to be determined approximately 2 weeks following the dose adjustment.

Details on the sampling of blood for determination of FVIII trough levels are presented in Section [21.3](#) and Section [21.4](#).

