Purpose for Change: 1) To also handle the case that the trough levels used for dose adjustment were due to different doses. The former formula would only handle the case of the same dose being used for all infusions as required per protocol. 2) To ensure that the dose is continuously aligned with the subject's weight changes, if applicable.

11. **Section 8.7.7, Treatment of Bleeding Episodes**
Description of Change: The anticipated recovery to be used in the absence of an individual recovery has been revised.
Purpose for Change: To be consistent with already approved prescribing information.

12. **Section 10.5.1, Patient Reported Outcomes**
Description of Change: Description of EQ-5D questionnaire amended to reflect 3 levels for each of the 5 measured dimensions.
Purpose for Change: Correction of error in original text.

13. Section 11.1.3, Hemophilia Joint Health Score (HJHS);

Section 11.1.4 X-ray of Impaired Joints;

Section 21.2, Detailed Flow Diagram of Study Procedures, Visits at Study Site;

Section 21.3, Schedule of Study Procedures and Assessments;

Section 23.3, Radiologic Classification of Changes

Description of Change: 1) The X-ray of an impaired joint was removed from Section 11.1.3 HJHS and a new Section regarding the conductance of an X-ray was added. 2) Definition for impaired joint requiring conductance of an X-ray was provided based on the HJHS scoring system. 3) Already existing X-rays of impaired joints not older than 12 months can be used. The repeat X-ray of the impaired joint after 12 months was removed. 4) The Pettersson Score was added to describe the radiologic findings.

Purpose for Change: 1) To account for the fact that X-ray is not part of the HJHS. 2) To provide a definition for a clinically impaired joint. 3) No radiologic changes are expected after 12 months of prophylactic treatment. 4) To have a consistent description of radiologic findings of the impaired joint.

14. Section 13.1, Immunogenicity;

Section 13.2.1.1, Serious Adverse Event

Description of Change: 1) In order to meet the definition of an SAE, the FVIII inhibitor has to be confirmed at the central laboratory. 2) Details were provided when to evaluate FVIII IgG subclass 1-4 and IgA, and IgE antibodies to FVIII and PEG-FVIII.

Purpose for Change: 1) To account for different threshold levels at the various local laboratories. 2) To provide instructions when to assess FVIII IgG subclass 1-4 and IgA as well as IgE antibodies.

15. Section 13.9.1.1, Blood Type

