Pharmacokinetic parameters at the initial PK assessment (prior to randomization) and at steady state (after the Month 9 visit; if applicable) will be summarized using descriptive statistics by assay type. Descriptive statistics for PK parameters are to include n, mean, SD, CV%, geometric mean, geometric CV%, minimum, median, and maximum, except that T_{max} should be reported with n, minimum, median, and maximum only.

In this study, individualized doses for the PK-guided dosing were calculated prior to randomization based on the terminal phase/ $t_{1/2}$ and IR of the initial PK assessment. During the study conduct, data changes that potentially affect the recommended dose and/or trough level assessments have been noted for some of the subjects in this study. Differences in PK parameters ($t_{1/2}$, IR) and the effect on dose recommendation and trough level calculations were assessed during study conduct and the effect on dose recommendation and trough level assessment was assessed. It was determined that the observed PK data changes have minimal impact on data integrity and that there is no material effect on medical and safety data of patients. Following database lock, differences in PK parameters ($t_{1/2}$, IR) between the initial and final analysis and the effect on dose recommendation and trough level calculations will be assessed again and subjects/data with changes will be presented in listings.

Incremental recovery at 15-30 minutes post infusion over time and FVIII activity trough levels after randomization will be summarized by treatment arm, assay, and scheduled visit using n, mean, SD, CV% minimum, median, maximum, geometric mean, geometric CV%, 1st quartile and 3rd quartile (Q1 and Q3, respectively), and IQR. Incremental recovery and FVIII activity trough levels will be displayed as boxplots by scheduled visit for the two treatment arms.

Box-plots for trough levels for each visit will be presented by assay. As the observed trough levels cannot necessarily be considered trough levels (e.g. due to deviation in sampling time from the individual planned interval), two analysis will be performed:

- For the primary analysis, trough levels will be calculated exactly to the end of the subjects' planned infusion interval using:

$$C_{trough,corrected} = C_{trough,measured} * 2^{\left(\frac{TAD-Interval}{t_{1/2}}\right)}$$

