where $C_{trough,corrected}$ is the calculated FVIII trough level at the end of the planned interval, $C_{trough,measured}$ is the observed FVIII activity, TAD is the time after the last infusion, and Interval is the individuals' planned interval. For a subject with a T hour infusion interval, trough samples that were collected outside of ± 16 hours (the reported half-life of BAX855) of the planned infusion interval, will be excluded from descriptive statistics and graphical representation.

- A secondary analysis will be performed using observed trough samples that are collected within a ± 2 hour of the planned interval (e.g., for a subject with T hour infusion interval, no infusion was given in the T-2 hours before the blood draw and there was exactly 1 infusion in the interval T+2 to T-2 before the blood draw; as an example, for a subject with a 48 hour infusion interval, no infusion has been given 46 hours before the blood draw and exactly one infusion has been observed between 50 to 46 hours before the blood draw).

Correlation of pre-infusion VWF:Ag and BAX 855 PK parameters $t_{1/2}$, MRT, $AUC_{0-\infty}$, AUC_{0-last} , CL, V_{ss} , and C_{max} of the initial and Month 9 PK assessment will be assessed by scatterplots and Spearman rank correlation coefficient.

Correlation testing between the average of various coagulation parameters (TGA parameters and FVIII trough levels) and ABR are discussed in Section 7.1.2: Bleeding Episodes.

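### As the text reads, the dose-adjustment formula in Protocol 8.7.6 weights the two troughs 0.5 and 1 instead of averaging them, so for equal troughs the high arm would be steered to about 6.67% rather than 10%

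*Protocol*

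**What the plan says.** Protocol 8.7.6 allows the regimen to be changed after an out-of-range trough has been confirmed by a repeat measurement, so two troughs are available. The new dose is the current dose times target trough over predicted trough, with targets of 10% (high arm) and 1.7% (low arm). The predicted trough "is the TL predicted for an infusion interval of" tau at the current dose, and is computed from "0.5 * \left(\frac{Dose_{current,\tau}}{Dose_1} * TL_{measured,t1} * 2^{\frac{t1-\tau}{HL}} \right) + \frac{Dose_{current,\tau}}{Dose_2} * TL_{measured,t2" with a half-life factor on the second trough as on the first.

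The formula covers low-arm troughs above 3% and, in the high arm, "FVIII levels >12% or <8% in the high dose arm, the adjusted dose for an infusion interval" tau. Low-arm troughs below 1% get a flat increase of about 30% instead. The Summary of Changes (item 10) gives the reason for the current formula: "To also handle the case that the trough levels used for dose adjustment were due to different doses".

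SAP 9.2 uses the same kind of half-life projection on a single trough, "C_{trough,corrected} = C_{trough,measured} * 2^{\left(\frac{TAD-Interval}{t_{1/2", and says the result "is the calculated FVIII trough level at the end of the planned interval".

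After a change, Protocol 8.7.6 requires a check: "Approximately 2 weeks after the dose adjustment, a repeat FVIII trough level determination at an additional study visit has to be performed". Protocol 12.3 repeats it: "a FVIII trough level has to be determined approximately 2 weeks following the dose adjustment". Section 8.7.6 also separately allows a higher dose or more frequent dosing when levels are under the lower limit.

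**The concern.** Each of the two terms already carries its own dose ratio and its own half-life projection, so each is by itself a full prediction of the trough at tau under the current dose. Combining two such predictions into one needs weights that sum to 1. As the text reads they are 0.5 and 1, which sum to 1.5. The bracket encloses only a product, where it does no work; it has a purpose only if it encloses both terms.

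This is the rule that brings high-arm subjects back to target in a trial that compares two target troughs. Followed literally, it would move them to a level that the same section treats as too low.

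**Working it through.** **Inputs.** From Protocol 8.7.6: targets 10% and 1.7%; high-arm triggers below 8% and above 12%; low-arm trigger above 3%. The documents give no worked example of this formula, so there is no plan figure to reproduce. The trough values below are illustrative.

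**Formulas.** A = (current dose / Dose1) x trough1 x 2^((t1 − tau)/HL), and B is the same for the second trough.
- Literal: P = 0.5A + B
- Average: M = 0.5(A + B)
- Dose factor = target / P or target / M
- Trough reached under the literal rule = target x M / P. This takes M as the true trough and assumes that trough scales with dose, as the formula itself does.

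**Consistency check.** Two troughs of 7%, drawn at tau after the current dose, should return 7%. Literal: 0.5 x 7 + 7 = 10.5%. Average: 0.5 x (7 + 7) = 7%.

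**High arm, equal troughs drawn at tau.**

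| Trough | Literal factor | Average factor | Reached, literal |
|---|---|---|---|
| 5% | 10/7.5 = 1.33 | 10/5 = 2.00 | 6.67% |
| 6% | 10/9 = 1.11 | 10/6 = 1.67 | 6.67% |
| 7% | 10/10.5 = 0.95 | 10/7 = 1.43 | 6.67% |
| 7.9% | 10/11.85 = 0.84 | 10/7.9 = 1.27 | 6.67% |
| 13% | 10/19.5 = 0.51 | 10/13 = 0.77 | 6.67% |

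The literal aim is 10/1.5 = 6.67% in every row. The factor falls below 1 only when the trough exceeds 6.67%, so for a trough flagged as low the direction reverses only between 6.67% and 8%. Re-applied at 6.67% it gives 10/(1.5 x 6.667) = 1.00, so repeating it would not correct the level.

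**Unequal troughs.** P/M = 1 + B/(A + B). For B/A of 0.5, 1 and 2 this is 1.333, 1.500 and 1.667, and the trough reached is 7.50%, 6.67% and 6.00%. It is below 8% when M/P < 0.8, that is, when B > A/3. The literal result also depends on order: 6% then 7.5% gives 10/10.5 = 0.952, while 7.5% then 6% gives 10/9.75 = 1.026. The average gives 10/6.75 = 1.481 either way.

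**Different doses, the case the amendment names.** Take 5.6% after 40 IU/kg and 7.0% after 50 IU/kg, with current dose 50 IU/kg and both drawn at tau. A = (50/40) x 5.6 = 7.0 and B = 7.0. Literal factor 0.952, average 1.429.

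**Low arm, above 3% only.** At 4%: literal 1.7/6 = 0.283, average 1.7/4 = 0.425. Trough reached 4 x 0.283 = 1.13%, inside 1-3%.

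**Draw time.** At 7% drawn 2 h early, with an assumed half-life of 12 to 18 h, the literal factor is 1.07 to 1.03 (average 1.60 to 1.54). Drawn 2 h late, it is 0.85 to 0.88 (average 1.27 to 1.32). The sign at 7% therefore depends on timing; the 1.5-fold ratio between the two readings does not.

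**The case against.** The strongest reply is that the whole point rests on one bracket in an equation read from PDF by a program. The supplied text seems to misread small characters elsewhere: in 21.4 the marker on the 7.5- and 10.5-month visits changes from q to e in the repeated table header, and in 21.3 the bleeding-episodes row carries a 1 where footnote i is evidently meant. A bracket closed too early on a long two-term expression would fit that pattern. This stands, and it cannot be settled without the original page.

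Second, the intent is plain. The definition of the predicted trough, the amendment rationale and the SAP projection all point to the average, and a pharmacokineticist would probably see the slip. That supports the proposed correction, but no other section restates the formula correctly.

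Third, the dose cut is a narrow case. At 5% or 6% the literal rule still raises the dose. In the second 6 months an adjustment for a low value needs a trough considerably below the limit, so 7% is a doubtful trigger there. A 4.8% cut may also vanish in the whole-vial rounding that 8.7.2 allows: for an assumed 70 kg at 50 IU/kg it is 3,500 x 0.048, about 167 IU, less than the smallest 250 IU vial. All of this is right, and it is why the 1.5-fold overstatement leads and the cut is secondary.

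Fourth, there are safeguards. The repeat trough at about 2 weeks would reveal a low value, and the separate provision for a higher dose or frequency could repair it even though re-applying the formula would not.

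A reader might go further and infer that high-arm subjects were under-dosed, that the contrast between arms was diluted, or that patients were harmed. The documents do not support that. The sponsor calculates the doses (8.7.3), adjustment details are in a separate document (21.3, footnote p), and starting doses came from the initial PK half-life and recovery (SAP 9.2), not from this formula.

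**Conclusion.** As the supplied text reads, the formula is wrong: it contradicts its own definition of the predicted trough. For equal troughs it overstates the prediction 1.5-fold, which moves the effective aim from 10% to about 6.67% in the high arm and from 1.7% to about 1.13% in the low arm. Only the high-arm result breaches a protocol limit. The reversal to a dose cut is confined to confirmed high-arm troughs of about 6.67% to 8% drawn at tau. These sizes assume equal normalised troughs and dose-proportional levels.

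Confidence is medium, because the bracket has yet to be confirmed on the original page. Use of the literal form, an effect on the comparison of arms and patient harm are all not shown. It is worth fixing because 8.7.6 presents this as how the adjusted dose will be obtained.

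**What to change.** 1. Check the bracket in section 8.7.6 against the original PDF. If both terms are enclosed there, the matter is closed.
2. If it is printed as supplied, issue a protocol clarification that moves the closing bracket: predicted trough = 0.5 x (A + B).
3. In that case, also confirm that the sponsor's dosing tool and the separate dose-adjustment document use the average.
4. Only if they do not, list the affected adjustments and show achieved troughs for those subjects by arm. SAP 9.2 already summarises troughs by arm, assay and visit, and already plans a post-lock listing of how PK data changes affected dose recommendations, so only the adjusted-subject subset is new.

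The cost is one bracket and a check of one tool and one document. No new data are needed. No view is taken here on the right dose for any subject.

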8.7.7 Treatment of Bleeding Episodes

BAX 855 ($10-60 \pm 5$ IU/kg) will be used for treatment of bleeding episodes (i.e., breakthrough bleeding episodes during prophylaxis) according to the guidelines in [Table 1](#). These guidelines may be adjusted by the investigator based upon his or her clinical judgment.

It is critical that treatment of a bleed is initiated as soon as possible after occurrence of the bleeding episode.

When bleeding is controlled, additional infusions of BAX 855 to maintain hemostasis are permitted, if required. Infusions given to maintain hemostasis should be documented in the eCRF.

For a detailed description of bleeding episodes into different sites see [Section 23](#).

^{viii} A target joint is defined as a single joint (ankles, knees, hips, or elbows) with ≥ 4 spontaneous bleeding episodes in any consecutive 6-month period.

Table 1 BAX 855 Treatment Guidelines for Bleeding Episodes		
Type of Bleeding Episode	FVIII Level Required (%) Dose (IU/kg)	Frequency of Dosing
Minor Early hemarthrosis, mild muscle bleeding, or mild oral bleeding, including, epistaxis	20 to 40% 10 to 20 (±5) IU/kg	Repeat infusions every 12 to 24 h for 1 to 3 days or until the bleeding episode is resolved
Moderate Moderate bleeding into muscles, bleeding into the oral cavity, definite hemarthrosis, and known trauma	30 to 60% 15 to 30 (±5) IU/kg	Repeat infusions every 12 to 24 h for 3 days or more until the pain and acute disability/incapacity are resolved
Major Significant gastrointestinal bleeding, intracranial, intra-abdominal, or intrathoracic bleeding, central nervous system bleeding, bleeding in the retropharyngeal or retroperitoneal spaces or iliopsoas sheath, fractures, head trauma	60 to 100% 30 to 60 (±5) IU/kg In case of life-threatening bleeds, a dose of 80 (±5) IU/kg may be considered	Repeat infusions every 8 to 12 h until the bleeding episode/threat is resolved

The required units will be calculated according to the following formula:

$$\text{body weight (kg)} \times \text{desired FVIII rise (\%)} \text{ (IU/dL)} \times \{\text{reciprocal of observed recovery}\}$$

Whenever possible, the subject's most recent individual IR should be used. In its absence, an anticipated recovery of 2.0 (IU/dL)/(IU/kg) should be assumed and the required units calculated using the following formula:

$$\text{body weight (kg)} \times \text{desired FVIII rise (\% or IU/dL)} \times 0.5 \text{ dL/kg}$$

The amount to be administered and the frequency of administration should always be oriented to the clinical effectiveness in the individual case.

In subjects with severe hemophilic arthropathy and/or target joints with recurrent bleeding requiring more than 2 infusions per bleed and/or where efficacy ratings are generally fair or none, an imaging technology such as MRI or an ultrasound of the affected joint(s) has to be applied to verify the presence of a bleed.

